9.3 POPULATIONS FOR ANALYSES

The primary and secondary endpoints will compare the JITAI group with the control group. Tertiary analyses may also compare important subgroups (e.g., caregiver groups that differ by relationship type [parent vs. spousal caregivers], caregiver groups that differ by sex [male vs. female caregivers], caregiver groups that differ according to the functional status of the person with TBI (e.g., complicated mild vs. moderate vs. severe TBI or perceived functional status based on Mayo Portland Adaptability Index scores).

The analyses will be an intention-to-treat approach where the participant will contribute data to the arm he/she was randomized to regardless of the amount of data contributed (i.e. the duration of participation).

9.4 STATISTICAL ANALYSES

9.4.1 GENERAL APPROACH

Continuous measures will be described using means and standard deviations (or medians and ranges if non-normality is detected), while categorical measures will be summarized with frequencies and percentages.

For inferential tests, a two group t-test with a 0.05 two-sided significance level will be used.

Analyses for primary, secondary, and tertiary endpoints are described individually, below.

The distribution of the data will be examined to ensure that parametric testing is appropriate. In cases where data distributions are not normal, nonparametric tests will be used to analyze the data.

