3 OBJECTIVES AND ENDPOINTS

Objectives	Endpoints
Primary	
Examine the efficacy of the JITAI to improve self-reported caregiver strain in care partners of persons with traumatic brain injury (TBI)	Change from baseline in self-reported caregiver strain as measured by TBI-CareQOL Caregiver Strain at the end of the 6-month (180 day) intervention period
Secondary	

Examine the efficacy of the JITAI to improve self-reported mental health (depression and anxiety) in care partners of persons with traumatic brain injury (TBI)	Change from baseline in self-reported depression as measured by PROMIS Depression at the end of the 6-month (180 day) intervention period
	Change from baseline in self-reported anxiety as measured by PROMIS Anxiety at the end of the 6-month (180 day) intervention period
Tertiary/Exploratory/Other	
All other objectives and endpoints (e.g. sleep and physical activity variables, other mental and physical health domains, etc.) are considered tertiary	

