6.2 FIDELITY

For this study, the intervention will be administered via the CareQOL app. The study team will conduct training during the baseline visit with each participant which will include:

- Helping the participant download and register for the CareQOL and Fitbit® apps on their personal device
- Helping the participant set any relevant app settings (e.g., make sure alerts are turned on/off, privacy settings, etc.)
- Demonstrating the CareQOL app features to the participant (e.g., participant dashboard, etc.)
- Ensuring that the participant understands the importance of entering the daily ratings and wearing the Fitbit®
- Explaining the relationship between the daily ratings and Fitbit® data and the intervention prompts (JITAI group only)
- Demonstrating how to sync the Fitbit® (including using the Fitbit® app) and how to enter the daily ratings in the CareQOL app

During the 10-day run-in period between the baseline visit and the start of the intervention, study team members will assist participants to make sure that participants can:

- Successfully wear and sync the Fitbit®
- Successfully respond to the EMA prompts

Participants who are unable to successfully complete the run-in period will be terminated from the study and noted as a screen failure.

Training and training materials will be provided to all study team members. New study members will undergo training before the study is started. Training will be documented in the electronic regulatory binder.

Participant adherence to the protocol will be assessed throughout the study. Study staff will have access to the CareQOL app dashboard which can be used to monitor participant engagement and adherence with the app. Specifically, study staff will monitor:

- Adherence to EMA entry
- Adherence to Fitbit® use/syncing
- Adherence to completing the end of month surveys (~30, 60, 90, 120, 150, 180 day)
- Adherence to completing the 3-month (~270 days) and 6-month (~360 days) post-intervention surveys

Adherence will be calculated as a percentage for each of these areas for all participants who are not withdrawn or lost to follow-up.

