9.2 SAMPLE SIZE DETERMINATION

Our initial power calculations were based on the expected difference in change in self-reported TBI-CareQOL Caregiver Strain (from baseline to 6-month follow-up) between the JITAI intervention group and the control group. Using self-reported TBI-CareQOL Caregiver Strain, we expect using a normative T-score, with a standardized mean set at 50 and a standard deviation of 9.66, the minimum detectable difference (MID) for caregiver strain to be in the range of 4-6 points. A sample size of 92 in each group will have 80% power to detect a difference in means of 4.0 assuming that the common standard deviation is 9.66 using a two group t-test with a 0.05 two-sided significance level.

Similar results would be expected for the expected difference in change in self-reported PROMIS Depression (from baseline to 6-month follow-up) between the JITAI intervention group and the control group. Using self-

Depression, we expect score, with a at 52.03 and a 9.79, the minimum (MID) for depression 4-6 points. A sample group will have 80%

Effect sizes (T-metric)	Correlation (ρ)				
	0.40	0.50	0.60	0.70	0.80
5	234	230	198	146	82
10	60	58	50	38	22
15	26	26	22	16	10

reported PROMIS using a normative T-standardized mean set standard deviation of detectable difference to be in the range of size of 95 in each power to detect a

difference in means of 4.0 assuming that the common standard deviation is 9.79 using a two group t-test with a 0.05 two-sided significance level.

Similar results would also be expected for the expected difference in change in self-reported PROMIS Anxiety (from baseline to 6-month follow-up) between the JITAI intervention group and the control group. Using self-reported PROMIS Anxiety, we expect using a normative T-score, with a standardized mean set at 54.8 and a standard deviation of 9.53, the minimum detectable difference (MID) for depression to be in the range of 4-6 points. A sample size of 90 in each group will have 80% power to detect a difference in means of 4.0 assuming that the common standard deviation is 9.53 using a two group t-test with a 0.05 two-sided significance level.

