9.4.2 ANALYSIS OF THE PRIMARY ENDPOINT(S)

Primary Endpoint: TBI-CareQOL Caregiver Strain Short Form (SF). TBI-CareQOL Caregiver Strain assesses perceived feelings of feeling overwhelmed, stressed and “beat-down” related to the care partner role. Self-reported responses are on a Likert scale. This measure is scored on a *T* metric (M = 50; SD = 10). Higher scores indicate more strain.

Self-reported TBI-CareQOL Caregiver Strain (T score) will be used to test the effectiveness of the JITAI. Change from baseline to 6-months post-intervention will be compared between the two arms. Means and standard deviations of the within-person changes will be calculated. In addition, we will model the dependent variable (Caregiver Strain) using linear mixed effect model, where a random intercept will be

NIH Behavioral and Social Intervention Clinical Trial Protocol Template v3.0 - 20180827

included to account for repeated measurements from the same subject. We include in the model the following independent variables: the randomization arm, time and interaction between randomization arm and time, and baseline Caregiver Strain T scores. Key biologic variables such as age, sex, TBI severity, and co-morbidities will be among some of the factors explored as potential confounders. Differences between treatment arms can then be obtained by estimating and testing the corresponding parameters in the linear mixed effect model.

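### The plan does not say whether the unadjusted t-test on change or the baseline-adjusted mixed model decides the trial, nor that the model test is the day-180 arm difference

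*Combined protocol and SAP*

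**What the plan says.** Section 3 defines the primary endpoint as "Change from baseline in self-reported caregiver strain as measured by TBI-CareQOL Caregiver Strain at the end of the 6-month (180 day) intervention period". Section 4.2 likewise places the primary outcome assessment at the end of home monitoring.

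Three places point to a t-test on change. Section 9.2 begins "Our initial power calculations were based on the expected difference in change in self-reported TBI-CareQOL Caregiver Strain" and sizes all three endpoints on a two-group t-test. Section 9.4.1 says "For inferential tests, a two group t-test with a 0.05 two-sided significance level will be used". Section 9.4.2 says "Change from baseline to 6-months post-intervention will be compared between the two arms".

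Section 9.4.2 goes on: "In addition, we will model the dependent variable (Caregiver Strain) using linear mixed effect model, where a random intercept will be" included. The model terms are "the randomization arm, time and interaction between randomization arm and time, and baseline Caregiver Strain T scores", and the paragraph closes "Differences between treatment arms can then be obtained by estimating and testing the corresponding parameters in the linear mixed effect model". Section 9.4.3 has the same structure for anxiety and depression.

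Two further statements bear on the choice. Section 9.4.1 replaces parametric tests by unnamed nonparametric ones if the data are not normal, with no rule for deciding that. Section 9.3 promises an intention-to-treat analysis in which people count in their assigned arm however much data they gave.

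**The concern.** Two analyses of the same endpoint both end in a test of arm, and neither is called primary or supportive. They use the baseline score differently and can disagree, and the plan has no rule for that case.

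The model itself is not fully specified. Time may be a visit category or a straight line. The visits may be the six monthly surveys or all eight post-baseline surveys. The parameters to be tested are not named. The time-point label in section 9.4.2 is also loose, because section 6.2 attaches the same label to a later visit: "Adherence to completing the 3-month (~270 days) and 6-month (~360 days) post-intervention surveys".

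Two things are at stake. If the t-test decides, the trial discards precision that the baseline score would give at no cost. If the decision waits until both results are known, the nominal 5% error rate no longer holds.

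**Working it through.** **Inputs from the documents.** Difference 4.0, SD 9.66, two-sided 0.05 and 80% power (section 9.2); T-score SD 10 (sections 8.1.5 and 9.2); up to 280 participants, 140 per arm (section 1.1); 15% attrition and correlations of 0.4 to 0.8 (the exploratory calculation in section 9.2, borrowed here).

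**1. The plan's own figure.** n per group = 2 × (1.960 + 0.842)² × 9.66² / 4.0² = 91.6, so 92, as stated. The same formula gives 95 for depression (SD 9.79) and 90 for anxiety (SD 9.53), also as stated. These figures are for the unadjusted t-test only.

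**2. Evaluable number (assumption).** 280 × 0.85 = 238, or 119 per arm.

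**3. Variance of the two comparisons.** With score variance σ² in both arms and at both times, and baseline-to-day-180 correlation ρ:
- change score: 2σ²(1 − ρ)
- day-180 score adjusted for baseline: σ²(1 − ρ²)
- ratio, adjusted to change: (1 + ρ)/2, which is never above 1

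The adjusted variance is therefore 30, 25, 20, 15 or 10% lower at ρ = 0.4, 0.5, 0.6, 0.7 or 0.8.

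**4. A coherent value of ρ.** Section 9.2 uses 9.66 for a difference in change but describes it as the SD of the score. Read as the SD of change, it implies a score SD of 9.66/√(2(1 − ρ)), which runs from 8.8 at ρ = 0.4 to 15.3 at ρ = 0.8. It agrees with a score SD of 10 only at ρ = 1 − 9.66²/(2 × 10²) = 0.53.

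**5. Power at ρ = 0.53 (noncentral t, 4 points, 119 per arm).**
- t-test on change: SD 9.66, noncentrality 4/(9.66 × √(2/119)) = 3.19, power 88.9%.
- baseline-adjusted: SD 9.66 × √0.767 = 8.46, noncentrality 3.65, power 95.3%.
- equivalent size for the t-test: 119/0.767 = 155 per arm.
- with 102 per arm (240 × 0.85 / 2), power is 83.7% against 91.9%.

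**6. Range if 9.66 is instead the SD of the score (119 per arm).**

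| ρ | t-test on change | baseline-adjusted |
|---|---|---|
| 0.4 | 82.7% | 93.5% |
| 0.5 | 88.9% | 95.7% |
| 0.6 | 94.5% | 97.8% |
| 0.7 | 98.4% | 99.4% |
| 0.8 | 99.9% | 100.0% |

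The gap nearly closes when the correlation is high.

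**7. Disagreement (simulation, complete data).** At ρ = 0.53 with a true 4-point effect, exactly one of the two tests is below 0.05 in about 7-8% of trials. With no effect and ρ = 0.6, at least one is below 0.05 in about 7%.

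**8. Why visits and time coding matter.** Suppose the benefit builds linearly to −4 at month 6 and then holds. A straight line through the arm differences at months 1-6, 9 and 12 (mean time 5.25, mean difference −2.75, slope −29.17/95.5 = −0.305 per month) gives −2.75 − 0.305 × 0.75 = −2.98 at month 6, where the truth is −4. If the benefit instead fades to zero by month 12, the line gives −1.96. With visit as a category, the month-6 difference is estimated directly. Both effect shapes are assumed for illustration.

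**The case against.** The strongest reply is that the hierarchy is clear enough. The general approach names the t-test, the sample size rests on it, the change comparison comes first, and the model is introduced as an addition. This is the natural reading, and it stands as far as it goes. But section 9.4.1 refers the reader to the individual endpoint descriptions, and those also test arm in the model. No sentence makes the model supportive.

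It also stands that the t-test is valid, that its power here exceeds the planned 80%, and that simply naming it primary would end the doubt about which test decides.

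A reader might infer four stronger points that the documents do not support:
- **That the model test could have no power.** An arm-by-time slope has about 5% power if the effect is constant from month 1, and an arm coefficient at day 0 has about 5% if the effect builds linearly. Neither targets day 180, which sections 3 and 4.2 fix as the endpoint. The fault is that the parameter is unnamed, not that the plan chose one of these.
- **That the primary time point is really about day 360.** Section 8.1.5.3 uses the post-intervention label for a day-180 survey, and section 4.2 settles the matter. This is loose wording.
- **That type I error is inflated.** The 7% in step 7 applies only if the better result is picked afterwards. The plan does not say that it will be.
- **That the t-test loses 42 of 280 people whom the model would keep.** 42 is 15% of 280, the number without a day-180 survey. Those with no post-baseline survey are lost to both analyses, and the documents do not say how many have earlier surveys.

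**Conclusion.** The concern holds as a gap in specification together with an avoidable loss of precision. The plan leans to an unadjusted t-test on change, also tests arm in a baseline-adjusted model, and leaves open which decides, how time is coded, which visits enter and which parameter is the day-180 effect.

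At the one correlation consistent with both stated SDs, baseline adjustment cuts the variance by 23% and raises power by about 6 percentage points. That figure assumes ρ = 0.53, equal variances, 119 evaluable per arm and a 4-point effect. Across the borrowed range of ρ the gain runs from about 11 points to almost none. The trial is adequately powered either way, so this should be corrected but does not threaten the trial.

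**What to change.** In sections 9.4.1 to 9.4.3, name one primary analysis for each endpoint:
- a mixed model on the monthly surveys at days 30 to 180, with arm, visit as a category, arm by visit, baseline T-score, and site (the randomisation lists are by site);
- an unstructured covariance, or robust standard errors, in place of reliance on a random intercept alone;
- a test of the arm difference at day 180.

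Make the change-score t-test and a rank-based test sensitivity analyses, and remove the normality-triggered switch for the primary test. Write day 180 in section 9.4.2, and in the parallel sentence of 9.4.3, to match sections 3 and 4.2. A baseline-by-visit term, a small-sample degrees-of-freedom correction and covariate-adjusted sensitivity models are optional.

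Naming the t-test as primary would also remove the ambiguity, but it would not recover the precision.

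The cost is a wording amendment to version 4.0, made before outcomes are compared by arm. No new data are needed, and the section 9.2 sample size can stand as conservative.

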9.4.2 ANALYSIS OF THE PRIMARY ENDPOINT(S)

Primary Endpoint: TBI-CareQOL Caregiver Strain Short Form (SF). TBI-CareQOL Caregiver Strain assesses perceived feelings of feeling overwhelmed, stressed and “beat-down” related to the care partner role. Self-reported responses are on a Likert scale. This measure is scored on a *T* metric (M = 50; SD = 10). Higher scores indicate more strain.

Self-reported TBI-CareQOL Caregiver Strain (T score) will be used to test the effectiveness of the JITAI. Change from baseline to 6-months post-intervention will be compared between the two arms. Means and standard deviations of the within-person changes will be calculated. In addition, we will model the dependent variable (Caregiver Strain) using linear mixed effect model, where a random intercept will be

NIH Behavioral and Social Intervention Clinical Trial Protocol Template v3.0 - 20180827

included to account for repeated measurements from the same subject. We include in the model the following independent variables: the randomization arm, time and interaction between randomization arm and time, and baseline Caregiver Strain T scores. Key biologic variables such as age, sex, TBI severity, and co-morbidities will be among some of the factors explored as potential confounders. Differences between treatment arms can then be obtained by estimating and testing the corresponding parameters in the linear mixed effect model.

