Primary Objective: Examine the efficacy of the JITAI to improve self-reported caregiver strain in care partners of persons with traumatic brain injury (TBI).

Secondary Objectives: Examine the efficacy of the JITAI to improve self-reported mental health (depression and anxiety) in care partners of persons with traumatic brain injury (TBI).

Endpoints:

Primary Endpoint: Change from baseline in self-reported caregiver strain as measured by TBI-CareQOL Caregiver Strain at the end of the 6-month (180 day) intervention period.

Secondary Endpoints: 1) Change from baseline in self-reported depression as measured by PROMIS Depression at the end of the 6-month (180 day) intervention period; and 2) Change from baseline in self-reported anxiety as measured by PROMIS Anxiety at the end of the 6-month (180 day) intervention period.

Study Population: Up to 280 care partners of persons with TBI will participate in this study. Participant recruitment and enrollment will take place at two data collection sites – the University of Michigan and Baylor College of Medicine. Care partners must be at least 18 years old, be able to read and understand English and be caring for an adult (age 18 or above) with a medically documented TBI who is at least 1 year post-injury who sustained their TBI at age 16 or older. They must be willing to use their personal mobile device (e.g., smartphone, tablet) for this study, be willing to download the study app (CareQOL) and Fitbit® app and be willing to complete all study assessments.

Phase or Stage: Not applicable; behavioral intervention.

[figure not shown]
Description of Sites Enrolling Participants: There are two data collection sites for this study: The University of Michigan in Ann Arbor, MI (n=120 care partners of persons with TBI) and Baylor College of Medicine in Houston, TX (n=160 care partners of persons with TBI).

Description of Study Intervention: Just-in-time adaptive intervention (JITAI) is a mobile health behavior-change approach that operationalizes the selection and delivery of personalized mobile device intervention strategies based on real-time data collection. In this study, a study-specific app (CareQOL app) will integrate sensor data from a Fitbit® (on physical activity and sleep) with real-time self-report ratings of HRQOL (caregiver strain, depression, anxiety) to inform the JITAI. The JITAI will deliver personalized messages via the app ~50% the days during the intervention period.

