4 STUDY DESIGN

4.1 OVERALL DESIGN

Study Design: This behavioral trial will use a two-arm randomized controlled design. Each of the up to 280 care partner participants will be randomized to an active “JITAI” arm or to a control arm. The random allocation of participants to the treatment arm or control arm establishes the basis for testing the statistical significance or difference between the groups in HRQOL (caregiver strain, depression and anxiety).

Randomization: Blocked randomization will be used to limit bias and achieve an equal distribution of participants to the control and treatment arms. A randomization list will be generated for each site and the study statistician will oversee randomization. The participant will be randomized once he/she is deemed eligible and has provided informed consent (i.e. at Enrollment prior to baseline data collection). The study coordinator/research assistant who consented the participant will use their site’s randomization list to assign the participant to the correct study arm.

Duration of Study Participation: Study participation for both arms of the study (control and JITAI) involves a baseline assessment, followed by an approximate 10-day run-in period then a 6-month (180 day) home monitoring period (in which the intervention will be administered to the JITAI group). After the completion of the 6-month (180 day) home monitoring period, post-intervention surveys will be administered at 3 months (90 days) and 6 months (180 days) after the end of the 6-month (180 day) home monitoring period. Thus, the total duration of the study is ~375 days.

Study Sites: This is a multi-site study involving two sites: University of Michigan and Baylor College of Medicine. University of Michigan is the lead site and their IRBMED will serve as the single IRB for this study.

Study Intervention: The just in time adaptive intervention (JITAI) uses sensor data derived from the Fitbit® (e.g., accelerometer-based estimates of physical activity and sleep) and real-time self-report ratings (assessed once daily) of HRQOL (caregiver strain, depression, anxiety) to deliver personalized “pushes” to participants via a study specific app (CareQOL app). The personalized pushes will be delivered on ~50% of the days over the 6-month intervention period.

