4.2 END-OF-STUDY DEFINITION

While the primary outcome assessment is at the end of the 6-month (180 day) home monitoring period, the end of the study is defined as completion of the final follow-up survey administered 6 months (180 days) after end of the home monitoring period shown in the Schedule of Activities (SoA), **Section 1.3.**]

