8.1.5.3 MONTHLY ASSESSMENTS

Participants will be prompted by the CareQOL app to complete a series of self-report surveys at the end of each month (day 30, 60, 90, 120, 150, 180) during the 6-month (180 day) home monitoring period. They will also complete a post-intervention/app feasibility survey at the end of month 6 (day 180). These surveys will be answered directly on the CareQOL app and/or by interview, and should take ~10-15 minutes to complete.

- Study Feasibility: At the 6-month (180 day) assessment only, participants will complete a Study Feasibility survey to assess the experience of the participant with the study methodology and technology, including the CareQOL app, Fitbit®, and the JITAi. Administration time is 5 minutes.

Additionally, participants will update their medical history, medications, therapies, and COVID history and be queried about AEs at the end of month 3 (day 90) and month 6 (day 180).

- Medical History, Medications, Treatments, COVID Questionnaire. Participants will update their medical history and current treatments/management strategies (medication and non-medication – e.g., exercise, mindfulness) and COVID history. Administration time for this assessment is 10 minutes
- Adverse Events. Participants will be asked about any changes in mental or physical health. Administration time is 5 minutes.

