9 STATISTICAL CONSIDERATIONS

9.1 STATISTICAL HYPOTHESES

Primary Endpoint:

1) We hypothesize greater decreases in caregiver strain will be observed among participants in the JITAI group (relative to the control group) at the end of the 6-month home monitoring period.

Secondary Endpoints:

1) We hypothesize greater decreases in anxiety will be observed among participants in the JITAI group (relative to the control group) at the end of the 6-month home monitoring period.

2) We hypothesize greater decreases in depression will be observed among participants in the JITAI group (relative to the control group) at the end of the 6-month home monitoring period.

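### The primary and secondary analysis text points to about day 360, while the endpoints and hypotheses are fixed at day 180

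*Combined protocol and SAP*

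**What the plan says.** **Endpoint definitions.** The synopsis (1.1) and the table in section 3 define the primary endpoint as "Change from baseline in self-reported caregiver strain as measured by TBI-CareQOL Caregiver Strain at the end of the 6-month (180 day) intervention period". Depression and anxiety are given the same time point. Section 3 makes everything else tertiary, beginning "All other objectives and endpoints". Section 4.2 separates the primary assessment from the end of the study: "While the primary outcome assessment is at the end of the 6-month (180 day) home monitoring period", with study completion tied to the final survey 180 days later. Each of the three hypotheses in section 9.1 concerns a greater decrease in the JITAI group ("relative to the control group) at the end of the 6-month home monitoring period").

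**Analysis text.** Section 9.4.2, for the primary endpoint, and section 9.4.3, for both secondary endpoints, carry the same sentence: "Change from baseline to 6-months post-intervention will be compared between the two arms". Each then adds a linear mixed model with arm, time, their interaction and the baseline score. No visit is named for the arm contrast.

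**How the protocol uses the term.** Section 4.1 gives the timing: "post-intervention surveys will be administered at 3 months (90 days) and 6 months (180 days) after the end of the 6-month (180 day". Section 6.2, in its list of what staff will monitor: "Adherence to completing the 3-month (~270 days) and 6-month (~360 days) post-intervention surveys". That list shows the end-of-month surveys, including day 180, as a separate item.

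**The concern.** The sentence that tells the analyst which change score to compare does not name the visit at which the endpoint is defined. Where the protocol attaches 6 months to a post-intervention survey, the date given is about day 360.

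The two visits answer different questions. Section 8.1.4.2 says intervention delivery stops when home monitoring ends. A day-180 contrast estimates the effect at the end of the intervention. A day-360 contrast estimates what remains 180 days after the last possible message.

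The assessment table in section 8.1.5 schedules the Caregiver Strain, Anxiety and Depression short forms at both visits, so the data will support either analysis. With two readings of the primary time point in one document, there is room to choose after the results are known, or to dispute which result is confirmatory.

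**Working it through.** **1. Day count, from the start of home monitoring.**

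- End of home monitoring and of the intervention: day 180 (sections 1.1, 3 and 4.1).
- 3 months post-intervention: 180 + 90 = day 270.
- 6 months post-intervention: 180 + 180 = day 360.

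The last two match the approximate day labels in section 6.2. The gap between the two readings is 360 − 180 = 180 days.

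**2. The statements side by side.**

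| Section | Outcomes covered | Time point |
|---|---|---|
| 1.1 Synopsis | primary and both secondary | day 180 |
| 3 Objectives and Endpoints | primary and both secondary | day 180 |
| 4.2 End-of-Study Definition | primary | day 180 |
| 9.1 Hypotheses | primary and both secondary | end of home monitoring, so day 180 |
| 9.4.2 Primary analysis | primary | 6 months post-intervention; literally about day 360 |
| 9.4.3 Secondary analysis | both secondary | 6 months post-intervention; literally about day 360 |

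**3. Does anything else in section 9 settle it?**

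- Section 9.4.1 names no time point and refers on to the endpoint-specific text.
- The mixed model uses repeated measurements with an arm-by-time interaction but does not say at which visit the arms are contrasted. Section 9.2, for the exploratory analyses, counts 8 post-baseline assessments. These are days 30, 60, 90, 120, 150, 180, 270 and 360, so both candidate visits are among the repeated measures.
- The power text in section 9.2 describes change to a 6-month follow-up. This is ambiguous rather than wrong: the schedule also uses follow-up for the day-360 visit, but marks that visit with a plus sign (sections 8.1.4.2, 8.1.5 and 8.1.5.4).

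**4. Do the sample sizes depend on the answer?** First reproduce the plan's figures. Inputs from section 9.2: difference 4.0; SD 9.66 (strain), 9.79 (depression), 9.53 (anxiety); two-sided alpha 0.05; power 80%; equal groups.

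n per group = 2 (z₀.₉₇₅ + z₀.₈₀)² SD² / difference², with (1.960 + 0.842)² ≈ 7.849 (from unrounded z values):

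- Strain: 2 × 7.849 × 93.32 / 16 = 91.6, rounded up to **92** (plan: 92)
- Depression: 2 × 7.849 × 95.84 / 16 = 94.0 (just above 94), rounded up to **95** (plan: 95)
- Anxiety: 2 × 7.849 × 90.82 / 16 = 89.1, rounded up to **90** (plan: 90)

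With the noncentral t distribution, power at those sizes is 0.798, 0.800 and 0.800. None of the inputs is tied to a particular day, so correcting the time point leaves the sample sizes as they are.

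**The case against.** The strongest reply is that the intended time point is not in real doubt. The endpoint sections and hypotheses agree on day 180, and no endpoint, objective or hypothesis names day 360. Sections 9.4.2 and 9.4.3 are there to analyse endpoints defined elsewhere, not to redefine them. The replacement rule (7.1) and the loss-to-follow-up rule (7.2) also turn on day 180.

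Usage of the term is not uniform either. Section 8.1.5.3 applies it to a day-180 form: "They will also complete a post-intervention/app feasibility survey at the end of month 6 (day 180"). Sections 5.5 and 6.3 date the later visits from the end of home monitoring without using the term. The sentence could therefore be read as meaning at 6 months, that is, once the intervention is over. The Schedule of Activities (1.3) was not in the text available for review and might show other visit labels.

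Most of this stands, and it makes a drafting slip the likely explanation. It does not remove the conflict. Section 6.2 puts the same interval and the same term at about day 360, and section 10.1.8 lists end-of-month assessments and post-intervention surveys as different things. An analyst working from section 9.4 must override its wording to test the stated endpoint. Visit labels in the Schedule of Activities would not change the sentence in section 9.4.

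A further objection is that prescribing the mixed-model contrast goes beyond the quoted error. Taking that contrast at day 180 only applies the endpoint already defined in section 3. It does not decide whether the t-test or the mixed model is primary, which is a separate question.

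**Conclusion.** The concern holds. As written, sections 9.4.2 and 9.4.3 specify a time point that, in the protocol's own labelling, is 180 days later than the one in the endpoint definitions and hypotheses. It affects all three primary and secondary outcomes. It must be corrected before analysis, because the sentence determines which data form the primary result and both sets of data will exist.

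The conclusion rests on reading the phrase as sections 4.1 and 6.2 use it. Day 180 is taken as the intended time point because every defining section gives it. No loss of power is claimed: the documents make no assumption about how much of an effect would persist to day 360, and the stated sample sizes reproduce.

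**What to change.** - In sections 9.4.2 and 9.4.3, state that the change compared is from baseline to the end of the 6-month (180-day) home monitoring period.
- Where the mixed model is used for these endpoints, specify that the arm difference is taken at day 180.
- State that the day-270 and day-360 contrasts are tertiary, consistent with section 3.
- In section 9.2, clarify that the 6-month follow-up in the power text means day 180.

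The cost is a wording change in two sections and a clarification in a third. No new data, additional participants or change to the sample size is needed.
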